6.4 General Concomitant Medication and Supportive Care Guidelines

6.4.1 Hematopoietic growth factors

Hematopoietic growth factors are not permitted on this study.

6.4.2 Management of anemia

Transfusion is acceptable for improving the hemoglobin value to ≥ 10 gm/dL to allow therapy to continue without delay. The patient should be assessed to rule out other causes of anemia. Use of erythropoiesis-stimulating agents is prohibited.

6.4.3 Management of diarrhea

Diarrhea is a commonly occurring toxicity with therapy for rectal cancer. With combination chemoradiation, it is anticipated that diarrhea is likely to occur. Without appropriate treatment, diarrhea can be prolonged, severe, and lead to dehydration and other complications (See Appendix F for clinical management of diarrhea and Appendix G for patient instructions for diarrhea management).

Patients who have multiple loose bowel movements and any worsening of fatigue, nausea, vomiting, right upper quadrant abdominal pain or tenderness, fever, rash, or eosinophilia should be promptly evaluated for changes in liver function (See Appendix G for sample patient instructions for diarrhea management).

Refer to the ASCO Recommended Guidelines for Treatment of Cancer Treatment-Induced Diarrhea for additional recommendations regarding diarrhea (Benson *et al.*, 2004).

Antidiarrheal medications:

All patients must be instructed to begin taking loperamide at the earliest sign of poorly formed or loose stools (\geq grade 1). Early intervention is important for patient safety.

Aggressive supportive care should be provided for patients with grade 4 ANC and \geq grade 3 diarrhea until neutropenia and diarrhea resolve. See Appendix F for clinical management of diarrhea. Hospitalization for evaluation and management of grade 3 or grade 4 complicated diarrhea, as defined in Appendix F, is strongly recommended.

All patients who experience diarrhea should be advised to drink liberal quantities of clear fluids. If sufficient oral fluid intake is not feasible, fluid and electrolytes should be substituted via IV infusion.

6.4.4 Management of nausea or vomiting

Grade 3 nausea and vomiting has been seen in early phase studies with capecitabine. Therefore, to optimize dose intensity and maintain quality of life, early initiation or prophylactic management with scheduled anti-emetic therapy (5HT-3 antagonists, metoclopramide, prochlorperazine) and/or lorazepam should be considered when patients begin treatment with

veliparib and capecitabine. In addition, management should include counseling regarding these toxicities and may include brief interruption of dosing or dose modification.

Investigators should also rely on standard clinical practice and guidelines for nausea management.

Antiemetic Therapy:

Antiemetic therapy should be administered according to National Comprehensive Cancer Network (NCCN) or American Society of Clinical Oncology (ASCO) clinical practice guidelines.

6.4.5 Mucocutaneous and Dermatologic Toxicity

Severe mucocutaneous reactions, some with fatal outcome, such as Stevens-Johnson syndrome and Toxic Epidermal Necrolysis (TEN) can occur in patients treated with capecitabine.

Capecitabine should be permanently discontinued in patients who experience a severe mucocutaneous reaction possibly attributable to capecitabine treatment.

Hand-and-foot syndrome (palmar-plantar erythrodysesthesia or chemotherapy-induced acral erythema) is a cutaneous toxicity. Median time to onset was 79 days (range from 11 to 360 days) with a severity range of grades 1 to 3 for patients receiving capecitabine monotherapy in the metastatic setting. Grade 1 is characterized by any of the following: numbness, dysesthesia/paresthesia, tingling, painless swelling or erythema of the hands and/or feet and/or discomfort which does not disrupt normal activities. Grade 2 hand-and-foot syndrome is defined as painful erythema and swelling of the hands and/or feet and/or discomfort affecting the patient's activities of daily living. Grade 3 hand-and-foot syndrome is defined as moist desquamation, ulceration, blistering or severe pain of the hands and/or feet and/or severe discomfort that causes the patient to be unable to work or perform activities of daily living. See Section 7.3 for details on capecitabine dose modification.

6.4.6 Prohibited Therapies

The following types of treatment, in addition to any cancer therapy other than the therapy specified in this protocol, are prohibited:

- **Chemotherapy**
Administration of chemotherapy other than the chemotherapy specified in this protocol is prohibited **prior to** resection of the primary rectal cancer.
- **Targeted therapy**
Administration of targeted therapy for malignancy is prohibited **prior to** resection of the primary rectal cancer.
- **Radiation therapy**
Administration of radiation therapy other than the radiation therapy specified in this

protocol is prohibited.

- **Live vaccines**

Live vaccines within 30 days prior to the first dose of trial treatment and while participating in the trial. Examples of live vaccines include, but are not limited to, the following: measles, mumps, rubella, varicella/zoster, yellow fever, rabies, BCG, and typhoid vaccine. Seasonal flu vaccines that do not contain live virus are permitted.

- **Systemic glucocorticoids**

Systemic glucocorticoids for any purpose other than to modulate symptoms from an event of clinical interest of suspected immunologic etiology. The use of physiologic doses of corticosteroids may be approved after consultation with the Principal Investigator.

Patients who, in the assessment by the investigator, require the use of any of the aforementioned treatments for clinical management should be removed from study treatment; however, patients should continue to be followed per protocol.

6.4.7 Drug/drug interactions

- **Phenytoin:** Increased phenytoin levels have also been reported in patients taking capecitabine concurrently with phenytoin and, therefore, need to be monitored.

Because there is a potential for interaction of IPdR with other concomitantly administered drugs, the case report form must capture the concurrent use of all other drugs, over-the-counter medications, or alternative therapies. The Principal Investigator should be alerted if the patient is taking any agent known to affect or with the potential for drug interactions. The study team should check a frequently-updated medical reference for a list of drugs to avoid or minimize use of. Appendix C (Patient Clinical Trial Wallet Card) should be provided to patients if available.

Interaction of IPdR with other drugs was not encountered in a previous trial of IPdR in patients with GI malignancies (Kinsella *et al.*, 2019). However, as stated above, the potential for such interactions and overlapping toxicities exists and will be closely monitored.

6.5 Duration of Therapy

In the absence of treatment delays due to AE(s), treatment may continue until study completion or until one of the following criteria applies:

- Disease progression
- Intercurrent illness that prevents further administration of treatment
- Unacceptable AE(s)
- Patient decides to withdraw from the study

- General or specific changes in the patient's condition render the patient unacceptable for further treatment in the judgment of the investigator
- Clinical progression
- Patient non-compliance
- Pregnancy
 - All women of childbearing potential should be instructed to contact the investigator immediately if they suspect they might be pregnant (e.g., missed or late menstrual period) at any time during study participation.
 - The investigator must immediately notify CTEP in the event of a confirmed pregnancy in a patient participating in the study.
- Termination of the study by sponsor
- The drug manufacturer can no longer provide the study agent

The reason(s) for protocol therapy discontinuation, the reason(s) for study removal, and the corresponding dates must be documented in the Case Report Form (CRF).

6.6 Surgery

Surgery must be performed within 8 to 12 weeks following the completion of study treatment.

6.7 Adjuvant Therapy

Per protocol, adjuvant therapy is not recommended but allowed at the investigator's discretion.

6.8 Duration of Follow-Up

Patients will be followed for 4 weeks after completion of study treatment, removal from study, or until death, whichever occurs first. Patients will be assessed at 4 weeks (approximately 30 days) following completion of IPdR (Week 10 unless there were delays in therapy). This will be the final assessment for study-related toxicity. Patients will undergo surgical resection 8-12 weeks following completion of study treatment, and study-related response will be assessed at that time. Patients removed from study for unacceptable AE(s) will be followed until resolution or stabilization of the adverse event.

7. DOSING DELAYS/DOSE MODIFICATIONS

7.1 IPdR Treatment Management

IPdR dose modifications are as follows:

Table 5: Part IA IPdR dose levels

Dose Level	IPdR Dose
1A (starting dose, Part IA)	75 mg PO BID
2A	150 mg PO BID
3A	300 mg PO BID
4A	600 mg PO BID
5A	1200 mg PO BID

Table 6: Part IB IPdR dose levels

Dose Level	IPdR Dose ^{1,2}
1B (starting dose, Part IB)	75mg QD
2B	150mg QD
3B	225mg QD
4B	300mg QD
5B	See Part IB dose escalation schema, Section 6.1.1

¹ The maximum allowed IPdR dose is 2400 mg QD.
² Actual doses will be rounded to account for availability of only 75 mg and 600 mg IPdR capsules.

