^aAttribution: 1 = unrelated, 2 = unlikely, 3 = possible, 4 = probable, 5 = definite.

^bRECIST criteria: NE, not evaluable.

[figure not shown]
^cDid not complete study therapy.

Pharmacokinetics analyses:

In the phase 1 trial, PK analyses demonstrated achievable and sustainable levels of plasma IUDR $\geq 1 \mu\text{M/L}$ (levels previously shown to mediate radiosensitization) at dose levels $\geq 600\text{mg/day}$ (Figure 4).

Figure 4: PK analyses – Phase 1 trial and pharmacology trial of oral IPdR as a prodrug for IUDR-mediated radiosensitization in patients receiving palliative RT for metastatic GI cancers (NCI #9882) (Kinsella *et al.*, 2019).

(A) Mean plasma concentrations of IUDR by IPdR dose level. (B) Plasma concentrations of IUDR in individual patients on Days 1, 15, and 22 at 1200 mg dose level (MTD, recommended phase 2 dose [RP2D])

Although not the primary objective of the study, all patients had measurable disease at study entry. Evaluation of target lesions within the radiation field 4 weeks following completion of therapy (at Week 8), using Response Evaluation Criteria in Solid Tumors (RECIST) criteria, revealed two Complete Response (CR), three Partial Response (PR), nine Stable Disease (SD), and no progressive disease (PD) in these patients.

In conclusion, this first-in-human tolerance study of IPdR confirmed that IPdR is predictably and readily absorbed following PO administration, is metabolized to IUDR principally by hepatic aldehyde oxidase, and demonstrates PK that compare favorably to those of IUDR. The administration of IPdR PO QD \times 28 days with RT is feasible and tolerable at doses that produce plasma IUDR levels $\geq 1\mu\text{M/L}$, achieving plasma IUDR levels that have previously been associated with clinically significant radiosensitization. This phase 1 study supports further testing of IPdR as a potential radiosensitizing agent. In this subsequent trial, we propose evaluating the addition of PO IPdR to preoperative capecitabine + RT for patients with rectal cancer.

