6.1.1 IPdR dose escalation schema

This is a phase 1 dose escalation study that consists of two parts, Part IA and Part IB. Part IA uses an accelerated titration design with a single patient cohort, and a 100% dose escalation between patient cohorts until a treatment related Grade 2 non-hematologic toxicity or grade 3 neutropenia or thrombocytopenia is observed. The accelerated titration design may reduce the number of patients potentially undertreated by receiving PO IPdR doses that are not expected to result in clinically relevant radiosensitization. After the completion of part 1A, the protocol will

be amended to incorporate the dose levels for part 1B. Part IB will commence when toxicity is encountered in Part IA. Cohorts of 3-6 patients will be entered per dose level until dose-limiting (DLT) is reached, and the MTD is defined. An IPdR dose of 2400 mg QD is the maximum allowed dose. Dose escalation between dose levels will be adjusted to accommodate the availability of 75mg and 600mg IPdR capsules.

Part IA:

An initial single patient dose escalation of twice daily PO IPdR × 38 days with concomitant capecitabine (825 mg/m²/BID Monday morning through Friday evening on RT days) will be conducted in Part IA. Dosing will be based on the patient's assigned dose level. The starting dose is 75 mg BID (Dose 1) × 38 days ($\geq 1/10^{\text{th}}$ MTD in ferrets, as previously determined [Kinsella *et al.*, 2000]). A 100% dose escalation will be used until a treatment related Grade 2 non-hematologic toxicity or grade 3 neutropenia or thrombocytopenia is observed. Two additional patients will then be entered at this dose level. If a second patient of these 3 patients experiences a treatment related Grade 2 systemic toxicity (or if a single patient develops treatment related \geq grade 3 toxicity), then a stop/switch rule is invoked for Part IA and Part IB of the dose escalation scheme commences. If not, the dose is incremented to the next level in Part IA (after each patient is evaluated for 4 weeks of follow up to assess acute toxicity).

Definitions of “Dose-limiting” and “Moderate” toxicities for Part IA (for exceptions see Section 6.2)

Grade 2 non-hematologic	Moderate
Grade 3 non-hematologic	DLT
Grade 4 non-hematologic	DLT
Grade 2 ANC and/or Plt	Moderate
Grade 3 ANC and/or Plt	Moderate
Grade 4 ANC and/or Plt	DLT

In part IA, if a patient develops:

- a DLT, the stop/switch rule is invoked, and part IB commences

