- a “moderate” toxicity, two additional patients will be entered at this dose level, and if
 - one of these patients develops a DLT, the stop/switch rule is invoked, and part IB commences
 - one of these patients develops a “moderate” toxicity, the stop/switch rule is invoked, and part IB commences
 - neither of the two additional patients develops a DLT or “moderate” toxicity, part IA recommences at the next dose level

A patient will be considered unevaluable if they receive $<67\%$ of their total intended dose of any study treatment (IPdR, capecitabine, or RT) for non-protocol required reasons. Patient medication diaries and RT documentation will be reviewed as each patient comes off-study to determine the actual total doses of each study treatment they received. If a patient is deemed unevaluable by this definition, they will be replaced by a new patient to be treated at the same intended dose level.

Part IA dose escalation schema			
Dose Level	Total radiation Gy (45 Gy primary field, 5.4 Gy [contact] Gy/fraction/day)	Capecitabine (mg/m² BID)	IPdR (mg BID) Administered throughout radiation
1A	50.4	825 mg/m ² BID	75 mg BID
2A	50.4	825 mg/m ² BID	150 mg BID
3A	50.4	825 mg/m ² BID	300 mg BID
4A	50.4	825 mg/m ² BID	600 mg BID
5A	50.4	825 mg/m ² BID	1,200 mg BID

BID – Twice Daily, RT – Radiation therapy

Part IA is closed to further accrual.

Part IB:

Under Part IB of this protocol, cohorts of 3-6 patients will be entered per dose level. In Part IB, 3 patients will initially be accrued to a dose level. If 0 of 3 patients do not experience grade 3 non-hematopoietic or grade 4 hematopoietic/GI DLT, then dose escalation will proceed. If a DLT is observed in one of the first 3 patients in a dose level cohort, the cohort will be expanded to a maximum of 6 patients.

Part IB dose escalation schema			
Dose Level	Total radiation Gy (45 Gy primary field, 5.4 Gy [contact] Gy/fraction/day)	Capecitabine (mg/m² BID)	IPdR (mg QD) Administered throughout radiation^{1,2}
1B	50.4	825 mg/m ² BID	75mg QD
2B	50.4	825 mg/m ² BID	150mg QD
3B	50.4	825 mg/m ² BID	300mg QD
4B	50.4	825 mg/m ² BID	600mg QD
5B	50.4	825 mg/m ² BID	1200mg QD
6B	50.4	825 mg/m ² BID	1800mg QD
7B	50.4	825 mg/m ² BID	2400mg QD

QD – Once Daily, BID – Twice Daily, RT – Radiation therapy

¹ The maximum allowed dose of IPdR is 2,400mg QD

² Actual doses will be rounded to account for availability of only 75 mg and 600 mg IPdR capsules

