6.2 Definition of Dose-Limiting Toxicity

Management and dose modifications associated with the above AEs are outlined in Section 7.

DLTs will be captured until 4 weeks after completion of IPdR therapy and will be graded according to the CTCAE v5.0. DLTs will be defined as clinically significant grade 3 or 4 toxicities possibly or probably related to study treatment.

- Grade 4 neutropenia (ANC < 500/mm³)
- Grade 4 electrolyte toxicities
- ANC <1000/mm³ with fever (temp >101 F) or infection
- Grade 4 thrombocytopenia: Platelets <25,000/mm³
- Platelets <50,000/mm³ requiring transfusion
- Grade 3 or 4 treatment related non-hematologic toxicities excluding alopecia.
- Patients who receive <67% of intended IPdR secondary to treatment related toxicities will also be considered as having a DLT

In addition, during chemoradiation, DLTs will also include AEs requiring interruptions of radiation for >5 consecutive scheduled fractions (and / or ≥ 9 total scheduled fractions) or for >10 consecutive scheduled doses of capecitabine (and / or ≥ 19 total scheduled doses of capecitabine). The following AEs will not be considered DLTs:

- Any grade of alopecia,
- Grade 3 arthralgia or myalgia,
- Brief (<1 week) grade 3 fatigue,
- Grade 3 fever,

- Grade 3 diarrhea or vomiting responding to supportive care
 - Grade 3 nausea, vomiting or diarrhea will be considered a DLT if it occurs for greater than 48 hours despite maximal medical support.
- Grade 3 radiation dermatitis,
- Grade 3 or 4 electrolyte abnormalities will not be considered DLTs if the electrolyte disorder can be corrected to grade 2 or less within 72 hours.

All patients who have received at least one dose of IPdR are evaluable for toxicities.

For dose escalation decisions, patients should have completed $\geq 80\%$ of the planned chemoradiation doses unless the reason for discontinuation is an AE that qualifies for DLT.

Dose escalation will proceed within each cohort in Part IB according to the following scheme. DLT is defined above.

Number of Patients with DLT at a Given Dose Level	Escalation Decision Rule
0 out of 3	Enter 3 patients at the next dose level.
≥ 2	Dose escalation will be stopped.

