7.3 IPdR and Capecitabine treatment management

Capecitabine and IPdR dose modifications are detailed in Table 7 and Table 8.

Additionally, the following dose modification instructions must be followed:

- All dose modifications should be based on the AE requiring the greatest dose modification.
- If RT is not administered (holiday, weekend, RT related toxicity, *etc.*), capecitabine is held; however, IPdR and RT continue per protocol unless otherwise contraindicated.
- If capecitabine and/or IPdR are held or discontinued, RT continues per protocol unless otherwise contraindicated.
- Capecitabine doses that have been reduced may not be escalated.
- IPdR doses that have been reduced may not be escalated.

Table 7: Capecitabine and IPdR dose levels

	Dose Level 0 Starting Dose (mg/m²)	Dose Level -1 (mg/m²)	Dose Level -2 (mg/m²)	Dose Level -3
Capecitabine	825 (BID) on days when RT is given	620 (BID) on days when RT is given	465 (BID) on days when RT is given	Discontinue
	Dose Level 0 Starting Dose	Dose Level -1	Dose Level -2	Dose Level -3

	Dose Level 0 Starting Dose (mg/m²)	Dose Level -1 (mg/m²)	Dose Level -2 (mg/m²)	Dose Level -3
IPdR	Part IA: Assigned dose level Part IB: see Table 6	Decrease one dose level (minimum dose is 75 mg QD; subjects requiring further dose reduction must have IPdR discontinued) See Tables 5 and 6 for Parts IA and IB dose levels	Decrease one dose level (minimum dose is 75 mg QD; subjects requiring further dose reduction must have IPdR discontinued) See Tables 5 and 6 for Parts IA and IB dose levels	Decrease one dose level (minimum dose is 75 mg QD; subjects requiring further dose reduction must have IPdR discontinued) See Tables 5 and 6 for Parts IA and IB dose levels

Table 8: Treatment management for capecitabine and IPdR

Important table instructions:

- Hold capecitabine and IPdR doses until any AE requiring dose modification returns to \leq grade 1 unless indicated otherwise in the treatment management sections/tables. If recovery to \leq grade 1 (or to other level specified) has not occurred after 3 weeks of delay, study therapy must be discontinued.
- All modifications in dose levels apply to both capecitabine and IPdR unless otherwise noted.

CTCAE v5.0 Adverse Event/Grade	Modifications for AEs that REQUIRED DELAY IN TREATMENT

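### Table 6 gives Part IB levels 3B and 4B as 225 and 300 mg QD, the Schema and 6.1.1 give 300 and 600 mg QD, and Table 7 sends dose reductions to Table 6

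*Combined protocol and SAP*

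**What the plan says.** Part IB dose levels are listed in three places. The Schema and Section 6.1.1 agree: 75, 150, 300, 600, 1200, 1800 and 2400 mg QD for 1B to 7B. In 6.1.1 the two rows at issue read "3B 50.4 825 mg/m ² BID 300mg QD 4B 50.4 825 mg/m ² BID 600mg QD".

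Table 6 in Section 7.1 agrees at 1B and 2B, then reads "3B 225mg QD 4B 300mg QD". Its 5B row carries no dose and says "See Part IB dose escalation schema, Section 6.1.1". It has no rows for 6B and 7B.

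Section 6.1 tells the reader to look in Section 7 for dose modifications. Within Section 7.3, Table 7 gives the IPdR starting dose as "Part IA: Assigned dose level Part IB: see Table 6". At each of the three reduction steps it says to go down one level and adds "See Tables 5 and 6 for Parts IA and IB dose levels". Section 6.1.2 doses by the assigned level and names no table.

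On step size, Section 6.1.1 says of Part IA: "A 100% dose escalation will be used until a treatment related Grade 2 non-hematologic toxicity". Section 9.1 describes the Part IB increment as more conservative than that.

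**The concern.** One level label carries two doses of the investigational agent, and the list that disagrees with the schema is the one that the dose-modification section tells sites to use. Reductions are foreseeable. Table 8 lowers the dose by one level at the first grade 2 or 3 diarrhea, and Section 6.4.3 expects diarrhea with this treatment. Two sites could therefore give different doses to patients in the same situation, each following the protocol.

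A rarer but larger problem would arise if a cohort were opened from Table 6. The primary objective is to find the MTD, and a result recorded only as 4B could then mean 300 or 600 mg.

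**Working it through.** **Inputs.** Schema list: Schema and Section 6.1.1. Table 6 list: Section 7.1. Treatment length: 38 days (regimen table). Capsule strengths: 75 and 600 mg (footnote to both lists).

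**Dose by label.**

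| Level | Schema / 6.1.1 (mg QD) | Table 6 (mg QD) | Ratio | 38-day total, schema vs Table 6 (mg) |
|---|---|---|---|---|
| 1B | 75 | 75 | 1.00 | 2,850 vs 2,850 |
| 2B | 150 | 150 | 1.00 | 5,700 vs 5,700 |
| 3B | 300 | 225 | 0.75 | 11,400 vs 8,550 |
| 4B | 600 | 300 | 0.50 | 22,800 vs 11,400 |
| 5B | 1200 | refers to 6.1.1 | – | – |

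**Could rounding explain it?** 225 = 3 × 75, 300 = 4 × 75 and 600 = 1 × 600. Every dose is exact, so the rounding footnote has nothing to act on.

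**Does the pointer to 6.1.1 settle it?** It stands in the 5B row only. Rows 1B to 4B carry their own doses.

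**First reduction by one level.**

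| Patient on | Look-up | Schema | Table 6 |
|---|---|---|---|
| 5B, 1200 mg | label | 600 mg (50% cut) | 300 mg (75% cut) |
| 4B, 600 mg | label | 300 mg (50% cut) | 225 mg (62.5% cut) |
| 3B, 300 mg | label | 150 mg | 150 mg |
| 3B, 300 mg | dose (300 mg is the 4B row of Table 6) | 150 mg | 225 mg |

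The 5B row matters most, because it is a factor of two. The last row runs the other way: Table 6 gives 225/150 = 1.5 times the schema dose, after a toxicity.

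**Escalation steps** (next dose / current dose − 1).

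- Schema: 75→150, 150→300, 300→600 and 600→1200 are +100% each; 1200→1800 is +50%; 1800→2400 is +33%.
- Table 6, then 5B from 6.1.1: 75→150 is +100%, 150→225 is +50%, 225→300 is +33%, 300→1200 is +300% (4-fold).

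**Against Section 9.1.** The first four schema steps equal Part IA's 100%, so they are not more conservative. Table 6 has smaller steps from 2B to 4B, but then a 4-fold step to 5B. Neither list fits Section 9.1 throughout, so that section does not show which was intended.

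**The case against.** The best defense is that the conflict does little harm in practice. The schema is printed twice. Section 13.1 requires the Principal Investigator to sign off escalation and de-escalation decisions through CTMS/IWRS, and Section 5.3.3.1 has IWRS handle slot assignment. A cohort opened at the wrong dose is therefore unlikely. The diary in Appendix D records capsules by strength, so an error could be traced. A reduction in one patient does not alter the dose assigned to the cohort, which is what the MTD rests on. Even the 4-fold step would end at 1200 mg QD, the recommended dose of the prior IPdR plus RT trial (Section 2.2.1.3), although that trial gave no capecitabine.

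It can also be said that the text does name a source for reductions, since Section 6.1 points to Section 7.

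Most of this stands, and it confines the point mainly to individual reductions. It does not remove it. The sign-off concerns cohort decisions and does not say which dose one patient gets after toxicity. Traceability shows an error afterwards but does not prevent it. And the pointer to Section 7 leads straight to the list that conflicts with the schema.

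A reader might infer that Table 6 is at least always the cautious choice. That is true for look-up by label but not for look-up by dose, as the 300 mg case shows.

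**Conclusion.** The current text is wrong as written: levels 3B and 4B each have two doses, in ratios of 0.75 and 0.50. The practical effect is on reductions: 300 against 600 mg from 5B, 225 against 300 mg from 4B at 600 mg, and 225 against 150 mg for a 300 mg patient looked up by dose. These figures assume only that a site applies Table 7 literally. The two-dose meaning of 4B and the 4-fold step need the further, unlikely event of a cohort started from Table 6.

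Two stronger readings are not supported:

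- **That the mismatch changes who counts as having a DLT.** Section 6.2 says "Patients who receive <67% of intended IPdR secondary to treatment related toxicities will also be considered as having a DLT", and a deeper cut lowers the amount received. But 6.2 does not say whether the intended amount is the assigned dose or the dose after a required reduction. On the second meaning the reduction itself does not count against the patient. Section 6.2 also already treats grade 3 nausea, vomiting or diarrhea lasting over 48 hours despite maximal support as a DLT, whichever table is used. No effect on DLT counts is claimed here.
- **That Table 6 defeats the purpose of the trial by taking patients under 600 mg.** Section 2.2.1.3 does report radiosensitizing plasma levels at 600 mg/day and above. But both lists place 1B to 3B below 600 mg by design, and the primary objectives are the MTD and toxicity.

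**What to change.** 1. Print one Part IB list in Table 6, covering 1B to 7B and matching 6.1.1: 75, 150, 300, 600, 1200, 1800 and 2400 mg QD. If Table 6 was what the sponsor intended, change the Schema and 6.1.1 instead.
2. Have Table 7 cite that single list for the starting dose and all reductions.
3. When choosing, reconcile the list with Section 9.1. If the schema stands, 9.1 should say that the steps up to 1200 mg are 100% and only the last two are smaller. If Table 6 stands, intermediate levels are needed between 300 and 1200 mg.
4. Report cohorts and the MTD in mg as well as by label.
5. Check in the diaries the mg actually given to any patient treated at, or reduced to, 3B or 4B.

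If the 6.1.1 values are kept, the cost is a wording amendment to Tables 6 and 7 and one sentence in 9.1, plus the diary check, with no added patients or procedures. Adopting Table 6 instead would cost more, because added levels could mean added cohorts.

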7.2.2 Management of IPdR for delay in radiation therapy

IPdR is administered either once daily or twice daily, 7 days a week, beginning with the first dose of capecitabine on Day 1. IPdR must be taken 7 days/week for the duration of radiation therapy (*i.e.* to be discontinued only following the final dose of radiation therapy). If radiation therapy is held, IPdR continues unless criteria for dose adjustment is met per Section 6.2. IPdR either once daily or twice daily, 7 days a week, will continue through the last dose of radiation therapy. Patients may receive up to 5 additional days (10 doses) of IPdR to accommodate delays in radiation therapy.

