Neutrophil count decreased: Grade 2 (1000- 1199/mm ³), 3, and 4	Hold capecitabine until \geq 1200/mm ³ . If recovery takes: 1 wk – maintain dose; 2-3 wks – \downarrow one dose level
Platelet count decreased: Grades 2, 3	Hold until \geq 75,000/mm ³ . If recovery takes: 1 wk – maintain dose; 2-3 wks – \downarrow one dose level
Grade 4	Hold until \geq 75,000/mm ³ . \downarrow one dose level

Important table instructions:

- Hold capecitabine and IPdR doses until any AE requiring dose modification returns to \leq grade 1 unless indicated otherwise in the treatment management sections/tables. If recovery to \leq grade 1 (or to other level specified) has not occurred after 3 weeks of delay, study therapy must be discontinued.
- All modifications in dose levels apply to both capecitabine and IPdR unless otherwise noted.

CTCAE v5.0 Adverse Event/Grade	Modifications for AEs that REQUIRED DELAY IN TREATMENT
GI : Diarrhea (despite optimal antidiarrheal management) Grades 2, 3	Treatment must be held for grades 2 and 3 diarrhea to avoid severe complications. 1 st occurrence – ↓ one dose level 2 nd occurrence – ↓ one dose level 3 rd occurrence – Discontinue
Grade 4	Discontinue
Mucositis - oral Grade 2	Maintain dose or ↓ capecitabine one dose level
Grade 3	↓ capecitabine one dose level
Grade 4	Discontinue capecitabine
Vomiting (despite antiemetics) Grades 2, 3	Hold and delay until \leq grade 1, then ↓ one dose level
Grade 4	↓ one dose level
Investigations (hepatic): Bilirubin, AST, alk phos Grades 2, 3	Hold until bilirubin returns to the baseline grade and AST and alk phos have returned to \leq grade 1; then ↓ one dose level
Grade 4	Discontinue chemotherapy
Febrile neutropenia: Grade 3	Hold until clinical resolution, then ↓ one dose level
Grade 4	Discontinue chemotherapy
Infection: Grade 2	Maintain dose or ↓ one dose level
Grade 3	↓ one dose level
Grade 4	↓ one dose level or discontinue
Nervous system disorders: Seizure Grades 1, 2, 3, 4	Any event of seizure, regardless of grade or attribution, requires discontinuation of IPdR and discussion with the PI regarding the decision to resume treatment.

Important table instructions:

- Hold capecitabine and IPdR doses until any AE requiring dose modification returns to \leq grade 1 unless indicated otherwise in the treatment management sections/tables. If recovery to \leq grade 1 (or to other level specified) has not occurred after 3 weeks of delay, study therapy must be discontinued.

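### Table 6 gives Part IB levels 3B and 4B as 225 and 300 mg QD where the Schema and Section 6.1.1 give 300 and 600 mg QD, and Table 7 makes Table 6 the source for starting doses and reductions

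*Combined protocol and SAP*

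**What the plan says.** The protocol states the Part IB dose ladder in three places. The Schema and Section 6.1.1 carry the same seven levels, from 75 to 2400 mg QD. Table 6 in Section 7.1 uses the same level labels but stops at 5B, whose entry is "See Part IB dose escalation schema, Section 6.1.1".

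Table 7 in Section 7.3 gives the source of the IPdR starting dose as "Part IA: Assigned dose level Part IB: see Table 6". For each reduction it says to go down one level and adds "See Tables 5 and 6 for Parts IA and IB dose levels". No text says which table governs if they differ.

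Reductions are triggered by Table 8. Its general instruction begins "Hold capecitabine and IPdR doses until any AE requiring dose modification returns to" and sets grade 1 or better as the recovery level; study therapy stops if recovery takes more than 3 weeks. For diarrhea that persists despite optimal antidiarrheal management, the table says "Treatment must be held for grades 2 and 3 diarrhea to avoid severe complications" and lowers the dose one level at the first occurrence. Unless noted otherwise, dose-level changes apply to both drugs.

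Delivered dose also enters the DLT definition in Section 6.2: "Patients who receive <67% of intended IPdR secondary to treatment related toxicities will also be considered as having a DLT".

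**The concern.** Two current tables attach different doses to the same level names, and the cross-references make the shorter, conflicting table the working one. In a multi-site trial, two sites could reduce patients in the same cohort to different doses, each while following the protocol.

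The inconsistency can also reach the primary endpoint. Grade 2 diarrhea is not in itself a DLT under Section 6.2, nor is grade 3 diarrhea that responds to supportive care. Such a patient can be held, reduced and kept in the escalation count. The size of the reduction then helps determine whether total IPdR falls below 67% of intended. In a 3+3 design, one patient reclassified as a DLT can expand a cohort or stop escalation.

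**Working it through.** **The ladders side by side (mg QD)**

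| Level | Schema and 6.1.1 | Table 6 |
|---|---|---|
| 1B | 75 | 75 |
| 2B | 150 | 150 |
| 3B | 300 | 225 |
| 4B | 600 | 300 |
| 5B | 1200 | refers to 6.1.1 |
| 6B | 1800 | no row |
| 7B | 2400 | no row |

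Table 6 is 25% lower at 3B (225/300 = 0.75) and 50% lower at 4B (300/600 = 0.50). The capsule-rounding footnote does not explain this, because every dose is exact: 225 = 3 × 75, 300 = 4 × 75, 600 = 1 × 600. Read with its own 5B cross-reference, Table 6 would jump fourfold from 4B to 5B (300 to 1200), against twofold in 6.1.1.

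**One-level reductions, assigned dose taken from 6.1.1 and levels matched by label**

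| From | To, by 6.1.1 | To, by Table 6 |
|---|---|---|
| 2B, 150 | 75 | 75 |
| 3B, 300 | 150 | 150 |
| 4B, 600 | 300 (−50%) | 225 (−62.5%) |
| 5B, 1200 | 600 (−50%) | 300 (−75%), only if the 4B row is used despite the 5B deferral |

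Reductions from 6B and 7B can be read only from 6.1.1, so the reduction targets differ at 4B and, on one reading, at 5B.

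**Illustration of the 67% rule.** The plan gives no figure to reproduce. Assumptions:
- Intended IPdR is 38 × the assigned dose. Section 6.2 does not define it.
- There is one hold of h days (3 or 7, both assumed), then one reduction.
- Held days are lost. Section 7.3 says "If capecitabine and/or IPdR are held or discontinued, RT continues per protocol unless otherwise contraindicated", and Section 7.2.2 ties the end of IPdR to radiation, "to be discontinued only following the final dose of radiation therapy".

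With d full-dose days and r = reduced dose / assigned dose:

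fraction = [d + (38 − d − h) × r] / 38

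It is a DLT when the numerator is below 0.67 × 38 = 25.46. Here r = 0.5 under 6.1.1 at both levels. Under Table 6, r = 225/600 = 0.375 at 4B and 300/1200 = 0.25 at 5B.

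*3-day hold*
- 6.1.1: 0.5d + 17.5 < 25.46, so DLT for d ≤ 15.
- Table 6 from 4B: 0.625d + 13.125 < 25.46, so DLT for d ≤ 19.
- Table 6 from 5B: 0.75d + 8.75 < 25.46, so DLT for d ≤ 22.

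*7-day hold*
- 6.1.1: 0.5d + 15.5 < 25.46, so DLT for d ≤ 19.
- Table 6 from 4B: 0.625d + 11.625 < 25.46, so DLT for d ≤ 22.
- Table 6 from 5B: 0.75d + 7.75 < 25.46, so DLT for d ≤ 23.

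| Level, hold | Days on which only Table 6 gives a DLT | Fraction at first day (6.1.1 vs Table 6) | Fraction at last day (6.1.1 vs Table 6) |
|---|---|---|---|
| 4B, 3 days | 16–19 | 67.1% vs 60.9% | 71.1% vs 65.8% |
| 4B, 7 days | 20–22 | 67.1% vs 63.5% | 69.7% vs 66.8% |
| 5B, 3 days | 16–22 | 67.1% vs 54.6% | 75.0% vs 66.4% |
| 5B, 7 days | 20–23 | 67.1% vs 59.9% | 71.1% vs 65.8% |

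**Long holds.** After a 13-day hold the most a patient can receive in 38 days is 25/38 = 65.8%, already under 67% on either ladder. No window remains at 13 days or more.

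**Extended courses.** Section 7.2.2 allows up to 5 more IPdR days. With 43 days given, the 5B windows for 3- and 7-day holds become 18–25 and 22–26 if intended dose also counts 43 days, or 11–20 and 15–21 if it stays at 38.

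**The case against.** The strongest reply is that the escalation doses are not in doubt: the Schema and 6.1.1 agree row for row, and no calculation in Section 9 uses Table 6. That stands. A reader might infer that cohorts would be assigned the wrong dose or that the MTD search is undermined. The documents do not support going that far. They show an ambiguous cross-reference for the starting dose and an ambiguous reduction target.

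Second, a reader might infer that a 5B patient would be cut from 1200 to 300 mg. Table 6's own 5B row sends the site to 6.1.1, where the next level down is 600 mg. Reaching 300 mg means going back to Table 6 for 4B, which is possible but less natural. The 4B conflict does not depend on that step.

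Third, the windows depend on short, assumed holds, while Table 8 permits up to 3 weeks. In every 38-day window above, the 6.1.1 patient also receives less than 80%. If the 80% completion requirement for escalation decisions in Section 6.2 covers IPdR, the contrast is between a DLT and a patient who may not count, not between a DLT and a clean non-DLT. The protocol expects diarrhea, but gives no frequency for diarrhea that persists despite optimal management. All of this limits the consequence; none of it removes the table conflict.

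Finally, a reader might infer that Section 9.1 is also wrong to call the Part IB increments more conservative, since 6.1.1 doubles the dose through 5B. In mg per day the description holds: Part IB steps are 75, 150, 300, 600, 600 and 600, against 150, 300, 600 and 1200 in Part IA. No change is needed there.

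**Conclusion.** The inconsistency is established from current text and needs no assumption: 225 versus 300 mg at 3B, 300 versus 600 mg at 4B, and no 600 mg, 6B or 7B row in the table that Table 7 relies on. The firm consequence for reductions is at 4B (300 versus 225 mg). At 5B it is conditional (600 versus 300 mg).

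The effect on DLT classification is possible rather than demonstrated. The day windows are illustrations that rest on the assumed hold lengths, the undefined intended dose and a single reduction. The point should be fixed because it concerns the dose of an investigational drug and costs almost nothing to correct.

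**What to change.** Replace the rows of Table 6 with the seven levels of Section 6.1.1: 75, 150, 300, 600, 1200, 1800 and 2400 mg QD for 1B to 7B. That is the natural direction, because the Schema and 6.1.1 agree and Table 6 already defers to 6.1.1 at 5B. Table 7's cross-references then work as they stand, and one-level reductions become 300 to 150, 600 to 300 and 1200 to 600 mg.

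The cost is a text correction to one table. No escalation dose in 6.1.1 changes and no patients are added. Section 9.1 can stay as written.
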